3.7.3. Prohibited concomitant therapy

Concomitant use of growth factors (including erythropoietin and excluding G-CSF and pegfilgrastim), cytotoxic chemotherapeutic agents (e.g. hydroxyurea), or other experimental drug or therapy for myelofibrosis while the subject is on study is prohibited. Filgrastim (G-CSF) is permitted for use during the study when used to treat febrile neutropenia or those who have \geq grade 3 neutropenia and at the investigators discretion for prolonged neutropenia. Chronic use (>2 weeks) of greater than physiologic doses of a corticosteroid agent (dose equivalent to >10 mg/day of prednisone) is not permitted during the study. Anagrelide is allowed to be used during the study to control elevated platelet count.

3.8. Discontinuation of Study Treatment

Subjects will receive oral CC-4047 daily from day 1 through day 28 every 28 days in the absence of disease progression or toxicity warranting discontinuation of therapy. Therapy will continue as long as there is a benefit, as judged by treating physician.

Treatment with study drug is to be discontinued when any of the following occurs:

- Lack of therapeutic effect
- Adverse event(s) that, in the judgment of the Investigator, may cause severe or permanent harm or which rule out continuation of study drug.
- Withdrawal of consent
- Lost to follow up
- Death
- Suspected pregnancy

3.9. Follow-Up

Subjects who discontinue treatment for any reason, will be followed every three months until disease progression or initiation of alternate therapy. At treatment discontinuation, subjects will undergo a safety assessment approximately 28 days post the last dose of study drug. In addition, off study evaluations per the Schedule of Assessments, Appendix M will be done.

4. SERIOUS ADVERSE EVENT REPORTING

4.1 Serious Adverse Event

An adverse event or suspected adverse reaction is considered "serious" if, in the view of either the investigator or the sponsor, it results in any of the following outcomes:

- Death
- A life-threatening adverse drug experience any adverse experience that places the patient, in the view of the initial reporter, at immediate risk of death from the adverse experience as it occurred. It does not include an adverse experience that, had it occurred in a more severe form, might have caused death.
- Inpatient hospitalization or prolongation of existing hospitalization
- A persistent or significant incapacity or substantial disruption of the ability to conduct normal life functions.
- A congenital anomaly/birth defect.

Important medical events that may not result in death, be life-threatening, or require hospitalization may be considered a serious adverse drug experience when, based upon appropriate medical judgment, they may jeopardize the patient or subject and may require medical or surgical intervention to prevent one of the outcomes listed in this definition. Examples of such medical events include allergic bronchospasm requiring intensive treatment in an emergency room or at home, blood dyscrasias or convulsions that do not result in inpatient hospitalization, or the development of drug dependency or drug abuse (21 CFR 312.32).

- Important medical events as defined above, may also be considered serious adverse events. Any important medical event can and should be reported as an SAE if deemed appropriate by the Principal Investigator or the IND Sponsor, IND Office.
- All events occurring during the conduct of a protocol and meeting the definition of a SAE must be reported to the IRB in accordance with the timeframes and procedures outlined in "The University of Texas M. D. Anderson Cancer Center Institutional Review Board Policy for Investigators on Reporting Unanticipated Adverse Events for Drugs and Devices". Unless stated otherwise in the protocol, all SAEs, expected or unexpected, must be reported to the IND Office, regardless of attribution (within 5 working days of knowledge of the event).
- All life-threatening or fatal events, that are unexpected, and related to the study drug, must have a written report submitted within 24 hours (next working day) of knowledge of the event to the Safety Project Manager in the IND Office. -
- Unless otherwise noted, the electronic SAE application (eSAE) will be utilized for safety reporting to the IND Office and MDACC IRB.

- Serious adverse events will be captured from the time of the first protocol-specific intervention, until 30 days after the last dose of drug, unless the participant withdraws consent. Serious adverse events must be followed until clinical recovery is complete and laboratory tests have returned to baseline, progression of the event has stabilized, or there has been acceptable resolution of the event.
- Additionally, any serious adverse events that occur after the 30 day time period that are related to the study treatment must be reported to the IND Office. This may include the development of a secondary malignancy.

Reporting to FDA:

Serious adverse events will be forwarded to FDA by the IND Sponsor (Safety Project Manager IND Office) according to 21 CFR 312.32.

It is the responsibility of the PI and the research team to ensure serious adverse events are reported according to the Code of Federal Regulations, Good Clinical Practices, the protocol guidelines, the sponsor's guidelines, and Institutional Review Board policy.

4.1.1. Expedited reporting by investigator to Celgene

Serious adverse events (SAE) are defined above. The investigator must inform Celgene in writing using a Celgene SAE form or MEDWATCH 3500A form of any SAE within 24 hours of being aware of the event. The written report must be completed and supplied to Celgene by facsimile within 24 hours/1 business day. The initial report must be as complete as possible, including an assessment of the causal relationship between the event and the investigational product(s), if available. Information not available at the time of the initial report (e.g., an end date for the adverse event or laboratory values received after the report) must be documented on a follow-up report. A final report to document resolution of the SAE is required. The Celgene tracking number (PO-MMM-PI-0011) and the institutional protocol number should be included on SAE reports (or on the fax cover letter) sent to Celgene. A copy of the fax transmission confirmation of the SAE report to Celgene should be attached to the SAE and retained with the patient records.

Celgene Drug Safety Contact Information: Celgene Corporation Global Drug Safety and Risk Management [name]

[contact]

[contact] E-mail:

4.1.2. Pregnancies

Pregnancies and suspected pregnancies (including a positive pregnancy test regardless of age or disease state) of a female subject occurring while the subject is on IP, or within (insert time-frame which must be at least 28 days of the subject's last dose of IP), are considered immediately reportable events. IP is to be discontinued immediately. The pregnancy, suspected pregnancy, or positive pregnancy test must be reported to Celgene Drug Safety immediately by facsimile, or other appropriate method, using the Pregnancy Initial Report Form, or approved equivalent form.

The female subject should be referred to an obstetrician-gynecologist, preferably one experienced in reproductive toxicity for further evaluation and counseling.

The Investigator will follow the female subject until completion of the pregnancy, and must notify Celgene Drug Safety immediately about the outcome of the pregnancy (either normal or abnormal outcome) using the Pregnancy Follow-up Report Form, or approved equivalent form.

If the outcome of the pregnancy was abnormal (e.g., spontaneous or therapeutic abortion), the Investigator should report the abnormal outcome as an AE. If the abnormal outcome meets any of the serious criteria, it must be reported as an SAE to Celgene Drug Safety immediately by facsimile, or other appropriate method, within 24 hours of the Investigator's knowledge of the event using the SAE Report Form, or approved equivalent form.

All neonatal deaths that occur within 28 days of birth should be reported, without regard to causality, as SAEs. In addition, any infant death after 28 days that the Investigator suspects is related to the in utero exposure to the IP should also be reported to Celgene Drug Safety immediately by facsimile, or other appropriate method, within 24 hours of the Investigator's knowledge of the event using the SAE Report Form, or approved equivalent form.

Male Subjects

If a female partner of a male subject taking investigational product becomes pregnant, the male subject taking IP should notify the Investigator immediately, and the pregnant female partner should be advised to call their healthcare provider immediately.

5. BIOSTATISTICAL ANALYSIS

5.1 Overview

This is two stage, phase II trial designed to assess the effect of CC-4047 and prednisone in subjects with Primary, Post Polycythemia Vera, or Post Essential Thrombocythemia Myelofibrosis (PMF, post-PV MF, or post-ET MF). Secondary objective is to determine the safety of CC-4047 and prednisone in this population.

5.2 Datasets to be analyzed

All subjects meeting the eligibility criteria that have signed a consent form and have begun treatment will be evaluable for response.

5.3 Statistical Methodology

5.3.1. Primary Endpoint

The primary endpoint of this trial is best overall response. An evaluable subject will be classified as a treatment success for the primary endpoint if the subject's best overall response is CR, PR or CI (Clinical Improvement) as determined by International Working Group Criteria over the first 6 cycles of study treatment at 0.5mg/day dose. The largest success proportion where the proposed treatment regimen would be considered unpromising in this population is 5%, representing the probability of a response by chance. The smallest success proportion that would warrant further subsequent studies with the proposed treatment regimen in this subject population is 20%.

5.3.2. Study Design

Subjects receiving CC-4047 alone, and the new study cohort of patients receiving CC-4047 and prednisone in combination will be evaluated using the same statistical design: a two stage design with one interim analysis will be used to permit early reporting of efficacy results if there is strong evidence that the study regimen is inactive. 37 evaluable subjects will be accrued onto this study unless undue toxicity is encountered. We anticipate accruing an additional 10-20% of subjects to account for ineligibility or cancellation; i.e. we may accrue as many as 70 subjects to this study. Subjects who have been taken off study due to toxicity related to high dose pomalidomide (i.e. those who started therapy with 3mg/day) will be replaced with new patients that will start therapy with 0.5mg/day), so that the goals of the study can be accomplished.

• Decision Rule: If 3 or fewer treatment successes are observed after all 37 evaluable subjects have been followed for at least 6 cycles, we will conclude that the treatment is insufficiently active in this subject population. If 4 or more treatment successes are observed, then this will be considered adequate evidence of promising activity, and the treatment may be recommended for further testing in subsequent studies.

- Over accrual: if more than the target number of subjects are accrued, the additional subjects will not be used to evaluate the stopping rule or used in any decision making process. However, they will be included in final point estimates and confidence intervals.
- Study duration: The anticipated accrual rate for this group of subjects is approximately 3 subjects per month. It will take approximately 14 months to accrue 37 evaluable subjects. The analysis can begin as soon as the 37th evaluable subject has been observed for 6 cycles (168 days), i.e., approximately 20 months after the trial opens.

5.3.3. Analysis Plan

Primary Endpoint

The observed response rate over the first 6 cycles of therapy at 0.5mg/day will be estimated by the number of responses (confirmed CR, PR or CI) over the first 6 cycles divided by the total number of evaluable subjects. Confidence intervals for the true response rates will be calculated according to the approach of Duffy and Santner.

Secondary Endpoints

Duration of response: duration of response is defined as the date at which the subject's objective status is first noted to be a CR, PR or CI to the date progression is documented (if one has occurred) or to the date of last follow-up (for those subjects who have not progressed).

Time to response: The time to response is defined as the time from study registration to the first date at which the subject's objective status was classified as a response (CR, PR or CI). In subjects who do not achieve a response, time to response will be censored at the subject's last evaluation date. The distribution for each of these event-time variables (duration of response and time to response) will be estimated by Kaplan-Meier curves.

Best overall response as determined by the International Working Group Criteria over the first 12 cycles of study treatment: will be estimated by the number of responses (confirmed CR, PR or CI) over the first 12 cycles divided by the total number of evaluable subjects. Confidence intervals for the true response rates will be calculated according to the approach of Duffy and Santner.

Cytogenetic responses and molecular response: cytogenetic responses and molecular responses will be summarized as well as evaluated graphically. Correlations among clinical responses and laboratory variables will be explored using a Wilcoxon/Kruskal-Wallis test for ordered contingency tables. Mutation status will be explored in relation to clinical outcome (response) using Fisher's exact test.

Quality of Life (QOL) assessments: For each of the QOL assessment components, changes from baseline to each of the follow-up time points will be reported. The change will be compared between two subgroups: subjects who response to the treatment and subjects who do not response. Normality testing via the Shapiro-Wilk procedure will determine whether or not parametric or nonparametric procedures will from the basis for analysis (two-sample t-test, Wilcoxon rank sum test).

Toxicity: As per NCI CTCAE Version 3.0, the term toxicity is defined as adverse events that are classified as either possibly, probably, or definitely related to study treatment. Such adverse events will be captured by Principal Investigator and his staff in a database. The maximum grade for each type of toxicity will be recorded for each subject, including start/stop dates, and frequency tables for each group will be reviewed to determine toxicity patterns. In addition, we will review all adverse event data that is graded as 3, 4, or 5 and classified as either "unrelated or unlikely to be related" to study treatment in the event of an actual relationship developing.

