There is previous human experience with the treatment of MMM by the original IMiD, thalidomide. Single-agent thalidomide at "conventional" doses (> 100 mg/d) has been evaluated in MMM based on its antiangiogenic properties and the prominent neoangiogenesis that occurs in MMM. Thalidomide monotherapy at such doses produces approximately a 20% response rate in anemia but is poorly tolerated (an adverse dropout rate of >50% in 3 months). To improve efficacy and tolerability, 21 symptomatic subjects (hemoglobin level < 10 g/dL or symptomatic splenomegaly) with MMM were treated with low-dose thalidomide (50 mg/d) along with a 3-month oral prednisone taper (beginning at 0.5 mg/kg/d). The combination therapy was well tolerated in all enrolled subjects, with 20 subjects (95%) able to complete 3 months of treatment. An objective clinical response was demonstrated in 13 (62%) subjects, all improvements in anemia. Among 10 subjects who were transfusion dependent, 7 (70%) improved and 4 (40%) became transfusion independent. Improvements in anemia correlated with lower pretherapy CD34⁺cell counts in the peripheral blood (median, 81.2 CD34+ cells/μL versus 554 CD34⁺ cells/ μ L [nonresponders]; P = 0.03) as well as lower numbers of circulating blasts (median, 0.8% versus 4.7% in nonresponders; P = 0.03). Among 8 subjects with thrombocytopenia (platelet count <100 x 10⁹/L), 6 (75%) experienced a 50% or higher increase in their platelet count. In 4 of 21 subjects (19%), spleen size decreased by more than 50%. Responses observed were mostly durable after discontinuation of the prednisone. The dose of thalidomide in this study (50 mg/d) was better tolerated than the higher doses used in previous studies. Adverse events associated with corticosteroid therapy were mild and transient. Clinical responses did not correlate with improvements in either intramedullary fibrosis or angiogenesis. The thalidomideprednisone combination was well tolerated and appeared to be a promising drug regimen for treating cytopenias in subjects with MMM.

Ten of the MMM subjects completed an additional 3 month thalidomide-only treatment phase of the study. After discontinuation of the prednisone, clinical responses were maintained in 62% in terms of anemia, 66% in terms of thrombocytopenia, and 50% of the splenomegaly responses. (Mesa, 2003)

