Prompted by the activity of single-agent oral lenalidomide (LEN) in primary or secondary (post-essential thrombocythemia or post-polycythemia vera) myelofibrosis (MF), Ouintas-Cardama and colleagues (2008) sought to evaluate the safety and efficacy of the combination of LEN and prednisone (LEN+PRD) in a phase II study for patients with MF. The rationale was that the potent antiangiogenic and cytokine-modulating activity of LEN may be enhanced by PRD to reduce marrow fibrosis and improve hematopoiesis in MF. Therapy consisted of LEN 10mg/d PO (dose level [DL] 0) on days 1–21 of a 28-day cycle in combination with PRD 30mg/d PO during cycle 1, 15mg/d during cycle 2, and 15 mg/d every other day during cycle 3. LEN was to be given for a minimum of 6 cycles and continued indefinitely in responders. LEN dose could be reduced to 5 mg/d (DL -1) or to 5 mg/d every other day (DL -2), or increased to 15 mg/d (DL +1) or 20 mg/d (DL +2) according to toxicity or lack of response. Forty patients (23 male) have been treated. Median age was 62 years (range, 41–86), time from MF diagnosis to LEN+PRD therapy 10 months (range, 0–122), WBC count 87x10⁹/L (range, 1.1–89), hemoglobin 9.8 g/dL (range, 7.8–17.3), and palpable splenomegaly 10cm (range, 0–25). Patients had received a median of 1 prior therapy (range 0-4), including hydroxyurea (n=14), azacitidine (n=6), thalidomide (n=4), and IFN- α (n=3). Ten (25%) patients were treatment-naïve. The JAK2^{V617F} mutation was detected in 18 (50%) of 36 tested patients and 20 (50%) of 40 had abnormal cytogenetics. 341 cycles have been administered. Patients have received therapy for a median of 18 months (range, 6–24.5). According to the International Working Group for Myelofibrosis Research and Therapy (IWG-MRT) criteria, 12 (30%) patients responded, including 8 JAK2^{V617F}-positive, 3 previously untreated, and 2 who had failed prior thalidomide-based therapy. Three (7.5%) partial response (PR), and 9 (22.5%) clinical improvement (CI) were seen. Anemia improved in 7 (30%; 3 PR and 4 CI) of 23 patients with pretreatment Hb <10g/dL or transfusion dependency. Splenomegaly significantly decreased in 10 (42%; 2 PR and 8 CI) of 24 patients. Again, few patients previously exposed to thalidomide responded to lenalidomide therapy. Responses occurred after a median of 12 weeks (range, 2–32), have been sustained for a median of 15 months (range, 4.1–20), and are ongoing in 10 of 12 responders still receiving LEN. After 12 months of therapy, a significant decrease was observed in the JAK2^{V617F} allele burden among the 8 JAK2^{V617F} positive responders (p=0.03). Four of the 8 JAK2^{V617F}-positive responders had >50% reduction of the mutant allele burden, becoming undetectable in 1. Serial histopathology analyses revealed significant reductions in bone marrow cellularity (p=0.01) and reticulin fibrosis (p=0.02) after 12 months of therapy in 8 assessable responders. The most frequent grade 3-4 toxicities were neutropenia (65%), anemia (50%), fatigue (30%), and thrombocytopenia (20%). Twentyfour (60%) patients required one dose level reduction (5 required further reduction to dose level -2), 1 (2.5%) had the dose escalated, and 15 (25%) remained at the initial dose level. Thirty (75%) patients discontinued therapy due to lack of response (n=15), pt's decision (n=3), grade 3–4 toxicity (n=9), allogeneic stem cell transplant (n=1), loss of response (n=1), and poor compliance (n=1). No transformation to acute myeloid leukemia has been observed. In summary, prolonged administration of LEN is generally well-tolerated, and yields long-lasting clinical, histopathological, and molecular responses in patients with MF when administered in a continuous manner.

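### Duration of response starts at CR, PR or CI but ends only at documented progression, so it is biased upward unless progression is defined to include loss of response

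*Combined protocol and SAP*

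**What the plan says.** Section 5.3.1 counts a subject as a success if the "best overall response is CR, PR or CI (Clinical Improvement) as determined by International Working Group Criteria" over the first six cycles. Section 5.3.3 uses the same scale to open the duration clock: "duration of response is defined as the date at which the subject's objective status is first noted to be a CR, PR or CI". It closes the clock on a different scale: "to the date progression is documented (if one has occurred) or to the date of last follow-up", the latter "for those subjects who have not progressed". The distribution "will be estimated by Kaplan-Meier curves".

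Documented progression is therefore the only event, and every other responder is censored at last follow-up whether or not the response is still present. The supplied text neither defines progression nor says whether losing a CR, PR or CI is a form of it. The IWG criteria are cited but not reproduced.

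Other sections treat absence of benefit and progression as separate states. Section 3.8 continues treatment in the absence of progression, yet lists lack of effect as its own reason to stop. Section 3.1 allows non-responders to come off at six months but keeps following them. Under Section 3.9, subjects who stop treatment for any reason "will be followed every three months until disease progression or initiation of alternate therapy".

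**The concern.** A response can end without the disease progressing. A subject who became transfusion independent and then needs regular transfusions again may simply be back at baseline. If that return is not scored as progression, Section 5.3.3 keeps the subject in response until progression occurs or follow-up ends, and Section 3.9 supplies the extra follow-up time.

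The error can go only one way. A progression-only end date can equal or follow the date the response was lost, but cannot precede it.

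The regimen makes this more than a technicality. Prednisone is given for three cycles and then stopped (Sections 3.1 and 3.5.2), and the combination is the reason for the new cohort (Section 1.2, 3/30/11 addendum). Whether responses survive the end of the steroid is a natural question for this trial, and duration of response is the endpoint that would answer it. Section 1.2 also quotes response durations from earlier studies, so this trial's figure is likely to be set beside them.

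**Working it through.** **The plan's own figures.** The documents give no planned value for duration of response. The two-stage design was recomputed to see whether it is touched (stop if 1 or fewer of 20; success if 4 or more of 37; exact binomial). It gives a significance level of 0.0898 and power of 0.9100, against 0.09 and 0.91 in Section 5.6. It reproduces, and it does not use duration.

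**Inputs for an illustration.**

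- Responders: 0.20 × 37 = 7.4, taken as 7 (target rate in Section 5.3.1, sample size in Section 5.3.2).
- Low loss share: 1/12 = 0.083. In the lenalidomide-prednisone study in Section 1.2, there were 12 responders and one discontinuation for loss of response. Its prednisone taper is the same as in Section 3.5.2.
- High loss share: 1 − 0.62 = 0.38. In the thalidomide-prednisone study in Section 1.2, after prednisone was stopped, "clinical responses were maintained in 62% in terms of anemia".
- Assumption: these losses occur without progression and are not scored as progression.

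**Scale of the bias before anyone progresses.** The curve as written reads 100% in response; the true proportion is 1 − s, where s is the loss share. The bias is s, compared with a simple binomial standard error, √[s(1 − s)/7].

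| | s = 0.083 | s = 0.38 |
|---|---|---|
| As written / true | 100% / 91.7% | 100% / 62% |
| Standard error | √(0.083 × 0.917/7) = 0.104 | √(0.38 × 0.62/7) = 0.183 |
| Bias in standard errors | 0.083/0.104 = 0.8 | 0.38/0.183 = 2.1 |
| Patients among 7 | 7 × 0.083 = 0.6 | 7 × 0.38 = 2.7 |

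**With progression also occurring.** Assume exponential time to progression, independent of loss, with all losses before month 6. The progression-only curve at 6 months is 0.5^(6/m) for median m, and the true proportion in response is (1 − s) times that. Neither median below comes from the documents.

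| Median to progression | As written | True, s = 0.083 | True, s = 0.38 |
|---|---|---|---|
| 12 months | 0.5^(6/12) = 0.71 | 0.917 × 0.707 = 0.65 | 0.62 × 0.707 = 0.44 |
| 24 months | 0.5^(6/24) = 0.84 | 0.917 × 0.841 = 0.77 | 0.62 × 0.841 = 0.52 |

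A simulation of 200,000 responders with s = 0.38, losses spread over months 0 to 3 and censoring over months 6 to 20, gives the same values to two decimals (0.71 against 0.44; 0.84 against 0.52).

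**Does censoring rescue it?** A subject who loses response may start alternate therapy, at which point follow-up under Section 3.9 ends. Censoring at the time of loss in the same simulation still gives 0.71 and 0.84. The Kaplan-Meier estimate then treats the lost responder as if still at risk and responding, so the bias remains under these assumptions.

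**The case against.** The strongest objection is that the argument turns on a definition that is not in view. Response is judged by IWG criteria. If their definition of progression, as applied here, includes loss of response, the gap narrows or closes. This stands, and it is why the point is conditional. A reader might infer outright that duration is overstated; the documents do not support that, because they do not show what progression covers. They do show that Section 5.3.3 leaves the matter unstated while Sections 3.1, 3.8 and 3.9 provide for subjects without benefit who have not progressed.

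A reader might also infer that 38% of responses will be lost without progression, a bias of about two standard errors. That is not supported either:

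- The figure comes from a different drug combination, and its denominator is not given; 8/13 and 5/8 both fit 62%.
- That study had 13 anemia responders, but only ten subjects completed the thalidomide-only phase. If the base is 13, at least three responders did not complete it. Responses not maintained may therefore include non-completers or progressions.
- The same paragraph describes responses as largely lasting after prednisone was stopped.
- The study with the matching taper reports 10 of 12 responses ongoing and a median of 15 months sustained. Pomalidomide responses are also described as durable.

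Nor does the separate listing of loss of response in the lenalidomide-prednisone study prove a distinction from progression. Its list of discontinuation reasons has no progression category, so it shows only that loss is a recordable outcome.

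Finally, duration is a secondary endpoint, described in about seven responders, with no test or threshold. That is correct and limits the consequence.

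**Conclusion.** The point holds in conditional form. As written, the end of a response is measured on a different scale from its start. Unless the definition of progression used in this trial includes loss of CR, PR or CI, the rule lengthens duration for every responder who loses the response first, and never shortens it.

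The size cannot be determined from the documents. About 0.8 to 2 standard errors with 7 responders is an illustrative range. It rests on loss shares borrowed from two other combinations and on the assumption that those losses were not progression. The bias is zero if every loss is also scored as progression. The six-month figures depend further on assumed progression medians and on independence of loss and progression.

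The response rate, the 4-of-37 rule, the significance level and the power are unaffected. The change should be made because the durability statement is what a reader will use to judge whether responses outlast prednisone.

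**What to change.** Replace the definition in Section 5.3.3 with wording such as:

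> Duration of response is the time from the first date a CR, PR or CI is noted to the earlier of (a) confirmed loss of response, meaning that no CR, PR or CI criterion is met, confirmed at a subsequent assessment and dated to the first such assessment, or (b) documented progression. Subjects with neither are censored at the last response assessment. Time to progression in responders is reported separately.

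The confirmation step matches the confirmed responses counted for the response rate and prevents one low hemoglobin or an isolated transfusion from ending a response. Section 5.3.3 should also state the definition of progression in use. If that definition already includes loss of response, saying so closes the point. The handling of death and alternate therapy is a separate gap that could be settled in the same edit.

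The cost is mainly wording, with no additional subjects. On treatment, visits and blood counts at least every 28 days (Section 3.1) supply much of the data. Off treatment, follow-up is every three months, so loss would be dated less precisely. The sponsor should check that those visits record what is needed to score response; the schedule of assessments was not in the text available for review. Reported duration may become shorter.
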